**Figure 1: Primary Efficacy Testing – Schematic Overview**

H0: null hypothesis; M: month; TNI: Target Number of Infections; VE: vaccine efficacy

Note that investigators and participants will remain blinded to their treatment assignment, at least until the last participant has reached the Month 30 visit or discontinued earlier.

Both the study's sample size as well as the TNI may be adjusted during the study, but prior to unblinding, to ensure sufficient power at the time of the primary analysis. Whereas adjustment of the sample size may be based on internal (but sponsor-blinded) study data (through monitoring of the pooled HIV-1 incidence) as well as on external study data (eg, Phase 2b HPX2008/HVTN 705), any adjustment of the TNI will solely be driven by data external to this study (eg, Phase 2b HPX2008/HVTN 705).

To cope with the dynamic environment of the development, approval and uptake of other prophylactic methods, such as PrEP (which would result in lower than expected annual incidence rates and thus lower study power), an estimated annual incidence rate in the control group of 2% was used to size this study.

[figure not shown]
Under the study assumptions described above, the study will also have approximately 80% power for the secondary efficacy endpoint VE(0-x months), assessing VE in the mITT population and accounting for all HIV-1 infections starting from Month 0 (Day 1).

### Rationale for the HIV-1 Incidence Assumptions

This study will recruit a large sample of highest-risk MSM and transgender individuals who have sex with men from many regions. In 2011, 62% of estimated new HIV diagnoses in the United States were attributed to male-to-male sexual contact; 39% of these MSM were black or African American (Cooley et al., 2014). Lifetime risk was 1 in 68 for males and 1 in 253 for females. Lifetime risk for men was 1 in 22 for blacks, 1 in 51 for Hispanic/Latinos, and 1 in 140 for whites. By risk group, the highest risk was among MSM (1 in 6) and the lowest was among male heterosexuals (1 in 524). Most of the states with the highest lifetime risk were in the South (Hess et al., 2017). Recent data from clinical studies show placebo incidence rates in high risk MSM of 6.6% in the Ipergay study (France, Canada; Molina et al., 2015), and 3.9% in the iPrEX study for high risk MSM (USA, Brazil, Peru, Ecuador, South Africa and Thailand, Grant et al., 2014). HVTN 505 yielded annual incidence rates of 2.3% in circumcised MSM and TG (USA; Hammer et al., 2013). To help identify the study participants, pre-trial assessments and data will be collected regarding incidence in potential sites.

The assumption of 2% annual HIV-1 incidence in the placebo group accommodates background PrEP use by assuming incidence is decreased by the person-years at risk during which PrEP is used, the efficacy of PrEP during PrEP use, and the adherence to PrEP use. [Figure 2](#) shows the impact of assumed PrEP use and adherence on annual HIV-1 incidence in the placebo group when the initial incidence (in the absence of PrEP) is 3% or 4% and the efficacy of PrEP is assumed to be 90%.

**Figure 2: Impact of Assumed PrEP use and Adherence on Annual HIV-1 Incidence in the Placebo Group**

HIV-1: human immunodeficiency virus type 1; PrEP: pre-exposure prophylaxis

The assumption of 3% annual incidence in the absence of PrEP, about 35% of person-years at risk during PrEP use, and 90% PrEP efficacy during use results in the assumed 2% annual placebo incidence rate.

A total sample size of 3,800 participants, as based on the efficacy endpoints, will also provide enough power for assessing safety of the vaccine regimen. The probability of observing at least one adverse event occurring at a rate of 1/100 is >99.9% with approximately 1,900 vaccinees. The probability of observing at least 1 adverse event occurring at a rate of 1/1,000 is 85% with approximately 1,900 participants. If no event is observed for a specific (serious) adverse event, then the Bayesian posterior probability that the adverse event rate is below 1/1,000 equals 95% for 1,900 participants and would provide us with 95% confidence that the true incidence is no more than 0.16%.

## 1.5. Randomization and Blinding

### *Procedures for Randomization and Stratification*

Participants will be randomly assigned to 1 of 2 treatment groups in a 1:1 ratio based on a computer-generated randomization schedule prepared before the study by or under the supervision of the sponsor. The randomization will be balanced by using permuted blocks and will be stratified by study site. Based on this randomization code, the study vaccine/placebo will be packaged and labeled for each participant.

Central randomization will be implemented in this study. The interactive web response system (IWRS) will assign a unique treatment code, which will dictate the treatment assignment and matching study vaccine/placebo vial for the participant. The requestor must use his or her own user identification and personal identification number when contacting the IWRS and will then give the relevant participant details to uniquely identify the participant.

### **Blinding**

The study participants, study-site personnel (except for those with primary responsibility for study vaccine preparation and dispensing), and investigator will be blinded to study vaccine allocation until the end of the study (see Section 10.1). The sponsor and its partners will be blinded to study vaccine allocation until the primary analysis, when the last participant has reached their Month x visit (with  $24 \leq x \leq 30$ ).

The pharmacist with primary responsibility for vaccine preparation (see CTP Section 14.3) will not be blinded to the study vaccine. In order to preserve blinding, he/she will place an overlay on the syringes. Administration of study vaccine to the participants will be performed by a blinded qualified healthcare provider from the study site.

The investigator will not be provided with randomization codes during the study. The codes will be maintained within the IWRS, which has the functionality to allow the investigator to break the blind for an individual participant.

Data that may potentially unblind the treatment assignment will be handled with special care to ensure that the integrity of the blind is maintained and the potential for bias is minimized. This can include making special provisions, such as segregating the data in question from view by the investigators, clinical team, or others as appropriate until the time of database lock and unblinding. Participants who discontinue vaccination early will be reminded that no HIV testing should be performed outside the study protocol to avoid unblinding.

Under normal circumstances, the blind should not be broken by the investigator until the end of the study and the electronic data capture (eDC) database is finalized unless it is essential for the timely management of the participant. In this case, the investigator may determine the identity of the treatment by contacting the IWRS. While the responsibility to break the code in emergency situations resides solely with the investigator, it is recommended that the investigator contacts the HPX3002/HVTN 706 safety review team if possible to discuss the particular situation, before breaking the blind. Telephone contact with the sponsor or its partners will be available 24 hours per day, 7 days per week. In the event the blind is broken, the sponsor and its partners must be informed as soon as possible. The date and reason for the unblinding must be documented by the IWRS, in the appropriate section of the case report form (CRF), and in the source document. The documentation received from the IWRS indicating the code break must be retained with the participant's source documents in a secure manner.

Participants who have had their treatment assignment unblinded due to safety reasons should continue to return for safety and immunogenicity evaluations and efficacy (see CTP Section 10.2), but will be withdrawn from further study vaccine administration.

## 2. GENERAL ANALYSIS DEFINITIONS

### 2.1. Study phases

A baseline (or reference) value will be defined as the value of the last available assessment prior to the first vaccination on Day 1.

The safety analysis will present all results by phase.

Study day or relative day is defined as follows:

Study Day = visit date - date of Day 1 + 1; if visit date  $\geq$  date of Day 1 (date of first vaccination).

Study Day = visit date – date of Day 1; if visit date < date of Day 1 (date of first vaccination).

#### 2.1.1. Phase definitions

The phases and periods in the study will be constructed as follows:

**Table 1: Phase and Period Definitions**

Phase	Phase number	Period	Period #	Interval	
				From	To
Screening	1			00:00 of the date of signing the informed consent form a	One minute prior to Dose 1 on Day 1
Regimen	2	Post-Dose 1	1	Date and time of first vaccination (Day 1)	Minimum of: 
 
a) 23:59 at the date of last contact (for early discontinuation)
 
b) 23:59 at the date of database cut-off date in case of an interim analysisc
 
c) 23:59 on 28 days after the first vaccination (23:59 of day of vaccination + 28 days)
 
d) One minute prior to post-dose 2
 

Follow-Up 1	3			One minute after Post-Dose 1 period end	Minimum of: 
 
a) 23:59 at the date of last contact (for early discontinuation)
 
b) 23:59 at the date of database cut-off date in case of an interim analysisc
 
c) 23:59 at the Date of last visit
 
d) One minute prior to post dose 2
 

Regimen	2	Post-Dose 2	2	Date and time of second vaccination (Day 85)	Minimum of: 
 
a) 23:59 at the date of last contact (for early discontinuation)
 

Phase	Phase number	Period	Period #	Interval	
				From	To
					
 
b) 23:59 at the date of database cut-off date in case of an interim analysisc
 
c) 23:59 on Day 28 after the second vaccination (23:59 of day of vaccination + 28 days)
 
d) One minute prior to post-dose 3
 

Follow-Up 2	4			1 minute after end of Post-Dose 2 period	
Minimum of:
 
 
a) 23:59 at the Date of last contact (for early discontinuation)
 
b) 23:59 at the date of database cut-off date in case of an interim analysisc
 
c) 23:59 at the Date of last visit
 
d) One minute prior to post-dose 3
 

Regimen	2	Post-Dose 3	3	Minimum of Date and Time of the two Dose 3 Injections (Day 169)	
Minimum of:
 
 
a) 23:59 at the date of last contact (for early discontinuation)
 
b) 23:59 at the date of database cut-off date in case of an interim analysisc
 
c) 23:59 on Day 28 after the second vaccination (23:59 of day of vaccination + 28 days)
 
d) One minute prior to post-dose 4
 

Follow-Up 3	5			1 minute after end of Post-Dose 3 period	
Minimum of:
 
 
a) 23:59 at the Date of last contact (for early discontinuation)
 
b) 23:59 at the date of database cut-off date in case of an interim analysisc
 
c) 23:59 at the Date of last visit
 
d) One minute prior to post-dose 4
 

Regimen	2	Post-Dose 4	4	Minimum of Date and Time of the two Dose 4 Injections (Day 337)	
Minimum of:
 
 
a) 23:59 at the date of last contact (for early discontinuation)
 
b) 23:59 at the date of database cut-off date in case of an interim analysisc
 
c) 23:59 on Day 28 after the second vaccination (23:59 of day of vaccination + 28 days)
 

Phase	Phase number	Period	Period #	Interval	
				From	To
Follow-Up 4	6			1 minute after end of Post-Dose 4 period	Minimum of: a) 23:59 at the Date of last contact (for early discontinuation) b) 23:59 at the date of database cut-off date in case of an interim analysis c c) 23:59 at the Date of last visit

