**NOTE:**

a The start time of screening phase is 00:00. In case an earlier date is available (e.g. for lab or vital signs then use the very first date in order to include all data)

b In case a dose is not administered, the observations end up in the previous Follow-Up phase

c For interim analyses a cut-off date will be identified: all data included in the analysis will go up to the cut-off date, any data referring to a later time point will not be included; ongoing events will be included and duration will be up to the cut-off date.

The periods/phases will be used primarily for safety. The post-dose periods (and the regimen phase) are considered active periods/phase, and the screening and follow-up phases are considered non-active phases for the evaluation of safety parameters. Efficacy endpoints will be calculated as described in Section 5.3.

For descriptive statistics over time, assessments (regardless of the investigated parameter) will be allocated to an analysis visit based on the visit number as captured in the database.

For participants who missed one or more doses but continued their planned visit schedule, the measurements after a planned but not administered dose will not be included in graphs and tables showing descriptive statistics over time. Those measurements will be shown in listings, but it will be indicated that these are not used in the analysis. Moreover, the vaccinations done after a missed vaccination will not be shifted to the previous vaccination but will be considered “as planned”: if for example the 2nd dose is missed, the 3rd dose vaccination will still be reported as post-dose 3.

Unless stated otherwise all analysis outputs will be shown by vaccine regimen (Vaccine vs Placebo).

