**Step 1: Allocation of events to the periods:**

Adverse events in the SDTM database are allocated to periods based on their start date/time. If the start date/time of an event falls between (or on) the start and stop date/time of a period, the AE is attributed to that period (treatment-emergent principle).

- In case of partial start or stop dates (i.e. time and/or day and/or month and/or year missing), the events are allocated to the periods using the available partial information on start and end date; no imputation will be done. If, for instance, the AE start date only month and year are available, these data are compared to the month and year information of the periods. This rule may lead to multiplication of the event as a consequence of its assignment to multiple periods.
- In case of a completely missing end date, the date is imputed by the cut-off date of the analysis for participants still ongoing in the study, and by the end date of the last period for participants who discontinued or completed the trial. In case of a completely missing start date, the event is allocated to the first active treatment phase (post dose 1 period), except if the end date of the AE falls before the start of the first active treatment phase (post dose 1 period).

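### SAP Table 1 gives Follow-Up 1 and Follow-Up 2 no end at a later dose when the next numbered dose is missed, so later adverse events can also be entered in an earlier follow-up phase

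*SAP*

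**What the plan says.** SAP 2.1 presents all safety results by phase, and Table 1 in 2.1.1 defines the phases. Each follow-up phase ends at the earliest of several limits: last contact (for early discontinuation), the cut-off of an interim analysis, the last visit ("23:59 at the Date of last visit") and, for the first three, the start of the next numbered post-dose period. That last limit is "One minute prior to post-dose 2" for Follow-Up 1, "One minute prior to post-dose 3" for Follow-Up 2 and "One minute prior to post-dose 4" for Follow-Up 3. Follow-Up 4 has no such limit because no dose follows.

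Two statements below the table deal with missed doses. Note b says: "In case a dose is not administered, the observations end up in the previous Follow-Up phase". The text then says that later vaccinations keep their planned number: "if for example the 2 nd dose is missed, the 3rd dose vaccination will still be reported as post-dose 3".

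SAP 4.2 Step 1 allocates events by when they start. If the onset lies within the limits of a period, "the AE is attributed to that period". SAP 3.9.2 reports concomitant therapies in each phase that their dates touch.

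**The concern.** The end of Follow-Up 1 depends on a dose that may never be given. If dose 2 is missed and dose 3 is given, Post-Dose 3 opens while Follow-Up 1 is still running. Follow-Up 2 has the same gap when dose 3 is missed and dose 4 is given. Note b says where observations go after a missed dose, but not when that stops.

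A programmer who follows Table 1 literally would put a serious event that occurs after dose 3 or 4 into the follow-up phase of dose 1, possibly two years after that dose, as well as into its proper period. A programmer who avoids this has to apply a rule that the SAP does not state. What is at stake is the accuracy of the follow-up rows in the by-phase safety tables and of the by-phase concomitant therapy tables.

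**Working it through.** The documents give no figure on this point, so the check applies the Table 1 rules to every dosing pattern and counts the days that fall in more than one period.

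**Inputs**
- Planned doses at Days 1, 84, 168 and 364, and the Month 30 visit at Day 910 (Protocol 9.1.2).
- End rules from SAP Table 1.
- Assumptions: no early discontinuation, no interim cut-off, last visit at Day 910, and each post-dose period ending 28 days after its own dose. Whole days are used, so a phase closed by a dose ends the day before it.

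**Formulas**
- A post-dose period runs from dose day s to s + 28, which is 29 days.
- The follow-up phase starts at s + 29. It ends the day before the next numbered dose if that dose was given, otherwise at Day 910.
- Days in two periods = 910 − (day of the later dose) + 1.

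**Dose 2 missed, dose 3 given.** Follow-Up 1 starts on Day 1 + 29 = 30 and runs to Day 910, which is 881 days. If it ended before dose 3 it would cover Days 30 to 167, which is 138 days. Overlap: 910 − 168 + 1 = 743 days (881 − 138 = 743).

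**Dose 3 missed, dose 4 given.** Follow-Up 2 starts on Day 84 + 29 = 113 and runs to Day 910, which is 798 days. If it ended before dose 4 it would cover Days 113 to 363, which is 251 days. Overlap: 910 − 364 + 1 = 547 days (798 − 251 = 547).

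Of the eight patterns of doses 2 to 4 given or missed, four produce overlap:

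| Doses given | Phase that overruns | Span under Table 1 | Days in two periods | Of these, in a post-dose period |
|---|---|---|---|---|
| 1, 3, 4 | Follow-Up 1 | Days 30–910 | 743 | 58 |
| 1, 3 | Follow-Up 1 | Days 30–910 | 743 | 29 |
| 1, 2, 4 | Follow-Up 2 | Days 113–910 | 547 | 29 |
| 1, 4 | Follow-Up 1 | Days 30–910 | 547 | 29 |

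The other four patterns (dose 1 only; 1 and 2; 1 to 3; all four) give zero overlap. No pattern puts a day in two post-dose periods. If each period ends just before the next dose actually given, all eight patterns have 0 overlapping days and 0 gaps.

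Table 1 itself prints Days 169 and 337 for doses 3 and 4. With those days the overlaps would be 910 − 169 + 1 = 742 and 910 − 337 + 1 = 574, so the conclusion does not depend on which schedule is used.

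**Effect on allocation.** An SAE starting on Day 250 in a participant with doses 1, 3 and 4 lies in Follow-Up 3 (Days 197–363) and also in Follow-Up 1 (Days 30–910). Step 1 is satisfied by both. Step 2 of SAP 4.2 combines overlapping or consecutive events with the same preferred term. It treats periods as following one another and does not address concurrent ones.

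**The case against.** The strongest reply is that the intention is already clear. The SAP says that a dose given after a missed one keeps its own number, so events after it belong to its own post-dose period. Note b can be read as covering only the time before that dose. Step 1 mentions multiplication of events only for partial dates, which suggests that a fully dated event was meant to have one period. Programming details are in the Data Presentation Specifications, which are not available here, so a double entry in the actual output is not shown. All of this stands: the overlap is a missing end rule, not an intended double count. It does not supply the rule, however, and Table 1 as written gives the wrong allocation.

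A reader might also infer more than the documents support:

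- **That every follow-up phase is affected.** No dose comes after dose 4, so Follow-Up 3 and Follow-Up 4 cannot overlap a later period.
- **That adverse events in general are double-counted.** SAP 4.2 always allocates solicited events to their post-dose period. The extra entry falls in a non-active phase, so Post-Dose 1 to 4 counts are unchanged. The post-any-dose summary (SAP 4) equals the regimen phase and counts a repeated event once.
- **That inflated follow-up person-time distorts the results.** SAP 4 and 4.1 report numbers and percentages of participants. No person-time denominator or exposure-adjusted rate is planned for safety.
- **That up to 5% of participants are involved.** The 5% in SAP 1.4 (0.05 × 3,800 = 190) is a planning assumption for any missed vaccination. Participants withdrawn from vaccination receive no further dose (Protocol 10.2) and create no overlap. A late dose 2 or 3 still closes the phase.

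**Conclusion.** The point holds for Follow-Up 1 and Follow-Up 2 only. On the planned schedule the overlap is 743 days when dose 2 is missed and dose 3 given, and 547 days when dose 4 is the first dose after a missed dose 3. These lengths assume follow-up to exactly Day 910. They are shorter for participants who leave early and longer for those followed beyond Month 30.

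The consequence is a wrong or duplicate entry of unsolicited AEs, SAEs, MAAEs, AESIs and concomitant therapies in the rows for an earlier follow-up phase. The same rule applies to both arms, and no active-period safety result or efficacy result changes. The participants involved are those who miss dose 2 or 3 and are then vaccinated again. Their number is not given, but on the planning assumption they are a subset of 5%. The priority is minor.

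**What to change.** - In the Follow-Up 1 and Follow-Up 2 rows of Table 1, replace item (d) with: one minute prior to the next vaccination actually administered. Follow-Up 3 and Follow-Up 4 need no change.
- Align note b: observations go to the previous follow-up phase only until that vaccination.
- Add to SAP 4.2 Step 1 that an event with a complete start date belongs to one period only. The existing provision for partial dates can stay.

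The cost is a few lines of SAP text and one line of period derivation. The rule does not depend on treatment. The amendment history dates study-level unblinding to 18 January 2023, before the current version, so the change should be recorded as a clarification made after unblinding. If the outputs already use such a rule, it is enough to document it. If they do not, the by-phase follow-up and concomitant therapy tables need to be rerun.

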- q Participants who have been prematurely withdrawn from study vaccine administration will be encouraged to complete the visit schedule as planned with assessments per the [Time and Event Schedule](#), including assessments of safety and HIV diagnosis. Participants who received the first 3 vaccinations but discontinue study vaccination before receiving the 4th vaccination, should continue the visit schedule as planned with assessments per the Time and Event Schedule including assessments of safety, immunogenicity and HIV diagnosis. They will also be reminded not to have HIV testing outside of the study protocol as this could lead to misdiagnosis and unblinding.
- r Participants will remain under observation at the study site for at least 30 minutes for presence of any acute reactions.
- s All participants will record solicited signs and symptoms in a diary for 7 days post vaccination.
- t Unsolicited adverse events will be recorded for all participants until 28 days after each vaccination.
- u Applicable from the time of local approval of protocol amendment 5 onwards: AESIs (including potential AESIs) are to be reported to the sponsor until 6 months after the last vaccination (see Section [12.3.4](#)). In case of a potential AESI of TTS, a serum sample should be obtained to test for anti PF4 at the local laboratory or substitute local laboratory, if possible; repeat testing may be requested for confirmation upon sponsor discretion. A test for anti PF4 will also be performed on a stored pre vaccination sample, if possible. Serious adverse events, MAAEs, and adverse events leading to discontinuation will be recorded until the participant's last study contact.
- v The site staff and the participant will make multiple efforts in good faith to be in contact after the last day of the reactogenicity period, or sooner if indicated, to discuss presence of any signs and symptoms of reactogenicity. Participants who self report any post vaccination reaction greater than mild are seen by a clinician within 48 hours after onset, unless the reaction is improving and/or has resolved completely.
- w The recall period of the questionnaire is the last month.
- x All participants will be asked about their level of absenteeism at each visit except for Visit 2a, 3a, 4a and 7a. At Visit 8, approximately 1 month post vaccination 4, participants will be asked about the acceptance of the vaccine regimen.

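### SAP Table 1 gives no phase to a safety event that starts after the last visit, more than 28 days after the last dose, and is reported at a later non-visit contact

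*SAP*

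**What the plan says.** SAP 2.1.1, Table 1, ends Follow-Up 1 to 4 at the minimum of:

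- "a) 23:59 at the Date of last contact (for early discontinuation");
- the database cut-off, if there is an interim analysis;
- "c) 23:59 at the Date of last visit";
- for Follow-Up 1 to 3, one minute before the next dose.

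The Post-Dose rows have no last-visit item. They run to 28 days after the dose (for dose 1: "c) 23:59 on 28 days after the first vaccination (23:59 of day of vaccination + 28 days")) unless last contact, cut-off or, for doses 1 to 3, the next dose comes first.

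SAP 2.1 states: "The safety analysis will present all results by phase". SAP 4.2, Step 1, gives the allocation rule: an event goes to a period when its start "falls between (or on) the start and stop date/time of a period, the AE is attributed to that period".

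The protocol's Time and Events Schedule, footnote u, says that serious adverse events, MAAEs and "adverse events leading to discontinuation will be recorded until the participant's last study contact". Protocol 9.4 foresees that reporting may include contact for safety follow-up.

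**The concern.** Protocol and SAP use different end points. Collection runs to the last contact. The phases that receive the collected events stop at the last visit.

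SAP 4 defines the SAE and MAAE endpoint over the whole course of the study. An event that is in the database but in no phase would be missing from the SAE, fatal-outcome and discontinuation counts, because those tables are built by phase. The participants concerned are mostly early leavers, who are the people most likely to have a gap between last visit and last contact. In a table of rare events, one omitted event is visible, and an entry in a listing does not correct the count.

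**Working it through.** **Inputs.** Table 1 and SAP 4.2 as above; visit days from Protocol 9.1.2; 3,800 participants and 10% annual dropout from SAP 1.4. I read the 28-day limit in each Post-Dose row as counted from the dose that opens that period, although the Post-Dose 3 and 4 rows refer to the second vaccination.

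**Step 1: which item decides.** Since last visit ≤ last contact, min(last contact, last visit) = last visit. The last-contact item never lengthens a Follow-Up phase.

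**Step 2: the rules applied literally.** Cases A, B, C and F have doses on days 1, 84 and 168. Post-Dose 3 then runs to day 168 + 28 = 196 and Follow-Up 3 starts on day 197.

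| Case | Last visit | Last contact | Event starts | Result |
|---|---|---|---|---|
| A | 273 | 330 | 310 | Follow-Up 3 ends at min(330, 273) = 273: no phase |
| B | 168 | 186 | 183 | Post-Dose 3: kept |
| C | 168 | 230 | 220 | Follow-Up 3 would run from day 197 to day 168: no phase |
| F | 330 (exit visit) | 330 | 310 | Follow-Up 3: kept |
| D, completer with four doses | 910 | – | 900 | Follow-Up 4: kept |
| E, completer with four doses | 910 | after 910 | 930 | no phase |

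**Step 3: is there a catch-all?** The special rules in SAP 4.2 cover partial dates and completely missing start or end dates. A note to Table 1 covers a dose not given. None covers a start after the last period has ended. There is also a side effect: for participants who left or completed, a completely missing end date is imputed with the end of the last period. An event such as A would then end before it began.

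**Step 4: size.** The plan states no figure that depends on this rule, so there is none to reproduce.

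- Early leavers by Month 30: 3,800 × (1 − 0.9^2.5) = 880. Person-years: 880 / (−ln 0.9) = 880 / 0.1054 ≈ 8,350.
- Assume the last contact is at dropout and no exit visit is attended. The intervals between scheduled visits and contacts (days 1, 9, 84, 92, 168, 176, 196, 273, 364, 372, 394, then 455 to 910 in steps of 91) total 909 days, and their squares sum to 71,877. Dropout spread evenly over time gives a mean gap of 71,877 / (2 × 909) = 39.5 days. Exponential dropout gives 39.0 days.
- Over 909 days there are 877 leavers and 8,324 person-years. The gap is 877 × 39.0 / 365 = 93.7 person-years, or 1.1%.
- Counting only gap days beyond 28 days after the last dose, the mean falls to 34.9 days: 877 × 34.9 / 365 = 83.9 person-years, or 1.0%.
- If half the leavers attend an exit visit on the last-contact date, this halves to about 0.5%.
- The documents do not give the real gap. If it ranged from 0 to 3 months for every leaver, the share would run from 0 to 880 × 3/12 = 220 person-years, or 220 / 8,350 = 2.6%.

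**The case against.** The best reply is that the last-contact and last-visit items were meant as alternatives: last contact for early leavers, last visit for completers. The literal reading makes the first item redundant, which supports that view, and the programming details sit in the Data Presentation Specifications, which are not available here. This may well be the intent. But Table 1 says minimum, and the last-visit item is not limited to completers. Even on this reading, case E stays without a phase.

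The other points limit the size, and they stand:

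- An exit visit is planned for early withdrawal (Protocol 9.1.8), and remote visits count as visits (Protocol 18). Either one, held on the last-contact date, closes the gap. Participants withdrawing consent may refuse the exit visit.
- A participant lost with no further contact has no gap.
- The person-time concerned lies in phases that the SAP calls non-active, and safety is descriptive with no formal testing.

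A reader might infer that every event after the last visit is lost. The documents do not support this: the Post-Dose periods have no last-visit limit (case B).

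A reader might also infer that most deaths vanish, or survive only in listings. That is not supported either. Allocation uses the onset date, so a fatal event that began before the last visit keeps its phase. Death is a listed reason for withdrawal (Protocol 10.2), and SAP 3.2 tabulates discontinuations by reason and vaccine group. SAP 4.1 adds listings or narratives. The documents give no mortality rate. Multiplying an assumed rate by all person-years would give total deaths, not lost ones.

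**Conclusion.** The gap in the rule is real and narrow. Read literally, Table 1 and SAP 4.2 leave without a phase any SAE, MAAE or event leading to discontinuation that meets three conditions: it starts after the last visit, it starts more than 28 days after the last dose, and it is reported at a later contact that is not a visit. Where the last visit falls within 28 days after the last dose, the Follow-Up interval is impossible.

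The expected loss is about 1% of person-time. This rests on the planned 10% dropout, on last contact falling at dropout and on no exit visits, so it is less wherever exit or remote visits are held. The plan assumes the same dropout in both groups, so there is no ground in the documents to expect an imbalance between arms. Primary efficacy, solicited events and the 28-day unsolicited tables are not affected. Minor severity, worth correcting because the correction is simple.

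**What to change.** In the Follow-Up 1 to 4 rows of Table 1, replace items (a) and (c) with one item for all participants: *23:59 at the latest of date of last visit, date of last study contact and date of death*. Keep the cut-off and next-dose limits, and leave the 28-day Post-Dose periods as they are.

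Add one sentence: an event that starts after the end of the last Post-Dose period, and on or before that date, is allocated to the Follow-Up phase after the last dose received. The sentence should name the Follow-Up phase explicitly, so that the boundary between the active Post-Dose period and the non-active phase stays clear.

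With this change, cases A and C go to Follow-Up 3. Case E goes to Follow-Up 4, provided the last contact or death is on or after day 930. Cases B, D and F do not move.

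The cost is SAP wording and one derivation, with no new data.
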